9.4.6. Subsequent Spinal Surgical Intervention

Some adverse events or treatment failures may lead to additional surgical interventions. Relatedness of these subsequent spinal surgical interventions will be assessed as described in the following sections.

9.4.6.1. Types of Subsequent Spinal Surgical Interventions

Secondary spinal surgeries (equivalent to subsequent spinal surgical interventions) will be classified using the definitions as specified in section 11.1 Table 7.

Any subsequent spinal surgical intervention will be reviewed by Medtronic safety to determine whether it is a true treatment failure. Subjects with a treatment failure will only be followed up for safety (AEs and subsequent spinal surgical interventions) and radiographic imaging (Qualitative assessments only: Risser score, device integrity and additional observations) until the patient reaches skeletal maturity.

Total events and total number of subjects who have additional surgeries will be summarized. The numbers

of revisions (total, preventive and non-preventive), removals, reoperations and other surgeries will also be summarized.

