5.2. Endpoints

5.2.1. Primary Safety Endpoint

The primary safety endpoint is any device-related adverse events up to 24 month follow up.

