9.4.5. Overcorrection

When the growth modulation occurs at a relatively rapid rate, the spine may grow past a corrected (e.g., 0 degree or neutral) alignment. This phenomenon is termed overcorrection as it represents an overshoot of the desired clinical account of a 0 degree Cobb angle. A negative main thoracic Cobb angle indicates reversal of the curve, i.e., from right-sided to left-sided curve.

The risk of overcorrection is mitigated by the following:

- Limiting enrollment to subjects with a Sanders Score equal or greater than 2 to allow sufficient growth time for the Braive™ GMS to correct the curve without allowing extra time for overcorrection.
- Requiring investigators to review the educational tool and to follow the surgical technique.
- The risk reduction is achievable by understanding the potential for a rapid growth spurt (e.g., Sanders score) and the surgeon's control to avoid excessive compression with the Braid (e.g., surgical technique). Prior to skeletal maturity, clinically significant overcorrection of the curve can be treated by removing the Braid or releasing tension by cutting the Braid, which will allow increased growth of the vertebrae on the operated side and may reduce the overcorrection. After skeletal maturity, clinically significant overcorrection of the curve can be treated by fusion surgery, which is the standard of care for skeletally mature patients who have failed bracing and were not treated with vertebral body tether. The potential sequelae for overcorrection are the same as those for scoliosis; however, the degree of overcorrection curvature is likely to be less than the degree of curvature at baseline. Potential complications include: cosmetic such as uneven shoulders, one hip or rib cage prominent, and body tilted to one side, low back pain, lower self-esteem, decreased social functioning, depression, persistent pain if there is wear and tear of the spine bones, spinal infection after surgery, spine or nerve damage from curve or spinal surgery, and lung and heart problems (in severe scoliosis with curves > 70 degrees).

If overcorrection occurs, it will be at the discretion of the physician, in consultation with the patient and family, to determine if surgical intervention is necessary. Overcorrection is considered clinically significant if it is greater than 20 degrees and/or if it requires a secondary spinal surgery classified as treatment failure and will be considered a device-related adverse event.

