10.2.3. During Post-operative Care

Clinical and radiographic assessments including collection of Adverse Events, Reoperations and Revisions/Removals will be performed prior to hospital discharge (immediate post-op), postoperatively at 3 months, 6 months, 12 months, 18 months and 24 months and annually thereafter until the subject reaches skeletal maturity (defined as Risser 5 as assessed by investigator), and as reported, regardless of follow-up interval. These assessments will mitigate the risks associated with the device including:

- Overcorrection Risk

The risk for overcorrection is the main risk with the anterior vertebral tethering procedure as many patients will experience a spine growth spurt after the device implantation. This growth spurt will render a faster spine deformity correction but also may increase the risk of overcorrection, which may require revision or removal. Therefore, follow up visits are scheduled at least every 6 months for the first 24 months following surgery and then annually until the subject reaches skeletal maturity (defined as Risser 5 as assessed by investigator). This provides the Investigators the opportunity to detect and treat curve corrections that may be approaching overcorrection.

- Other Device and/or Procedure-Related Risks

Medtronic Controlled Information

Other reported risks with the procedure are implant loosening and implant failure, which may require revision or removal. The follow up visits that are scheduled until the subject reaches skeletal maturity ensure that these potential risks will be detected and can be treated before they have progressed.

- Radiation Exposure Risk

Subjects will be exposed to radiation from X-rays taken during follow-up visits. However, some of these X-rays would likely be taken as standard of care for this condition, regardless of whether the patient was in the study. The ALARA (as low as reasonably possible) principles of reducing radiation exposure to the subjects enrolled will be recommended to all sites participating in the BRAIVE IDE study.

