Moderate (Grade 2): Minimal, local or noninvasive intervention indicated; limited age appropriate instrumental activities of daily living (preparing meals, shopping, using the phone, managing

money, etc.).

Severe (Grade 3): Severe or medically significant but not immediately life-threatening; hospitalization or prolongation of hospitalization indicated; disabling; limiting age appropriate self-care activities of daily living (bathing, dressing and undressing, feeding self, toileting, taking medications, and not bedridden).

Life Threatening (Grade 4): Life threatening consequences; urgent intervention indicated; death.

SUBSEQUENT SPINAL SURGICAL INTERVENTION

Subsequent spinal surgical interventions will be classified using the following definitions, based on the description provided:

- Revision is a procedure that adjusts, or in any way modifies or removes, *part* of the original implant configuration, with or without replacement of a component. A revision may also include adjusting the position of the original implant configuration. Revisions will be considered in two categories:
 - Preventive surgery: Any braid manipulations (e.g., cutting or loosening the braid). *Preventive surgery for overcorrection will not be considered a treatment failure*
 - Non-preventive surgery: The revision is the result of an adverse event, i.e., the initial positioning of the device contributed to the adverse event and must be repositioned, or additional instrumentation is added to the original implant configuration. *Non-preventive surgery will be considered as a treatment failure.*
- Removal is a procedure where *all* of the original system configuration is removed with or without replacement. *Removal surgery will be considered a treatment failure.*
- Reoperation is a surgical procedure at the study treatment level(s) that does not involve removal, modification, or addition of any components to the original system. Examples include debridement of a surgical wound, scar revision or evacuation of a hematoma. *These will not be considered a treatment failure.* Spinal fusion or extension of the fixation due to the progression of initial scoliosis *will be considered a treatment failure.*
- Other is any other subsequent spinal surgical procedure not classified as a revision, removal or reoperation. Examples include spinal surgery not at the study treatment level(s) such as microdiscectomy or hernia repair.

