11.4. Device Deficiencies

A device deficiency (DD) is an inadequacy of a medical device with respect to its identity, quality, durability, reliability, safety or performance. Device deficiencies include malfunctions, use errors, and inadequate labeling. All device deficiencies must be documented and submitted to Medtronic on the Device Deficiency eCRF. In addition, the investigator must also determine and document on the eCRF device deficiencies that did not lead to adverse event but could have led to a serious adverse device effect:

- If either suitable action had not been taken,
- If intervention had not been made, or
- If circumstances had been less fortunate
- Refer to Table 10 for investigator reporting timelines for device deficiencies.

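### After a treatment failure the protocol no longer requires a Cobb angle, although overcorrection above 20 degrees is a device-related adverse event and some failures can leave a tether in a growing child

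*Protocol*

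**What the plan says.** Protocol 9.4.6.1 sets the follow-up of a child whose further spinal surgery has been confirmed as a treatment failure: "Subjects with a treatment failure will only be followed up for safety (AEs and subsequent spinal surgical interventions) and radiographic imaging". The imaging carries its own limit: "Qualitative assessments only: Risser score, device integrity and additional observations". Both apply until skeletal maturity.

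Protocol 9.4.5 defines the overcorrection that counts: "Overcorrection is considered clinically significant if it is greater than 20 degrees and/or if it requires a secondary spinal surgery classified as treatment failure". Such overcorrection "will be considered a device-related adverse event". Protocol 5.2.1 reads: "The primary safety endpoint is any device-related adverse events up to 24 month follow up". Section 13.6.1 and SAP 7.10.1 add a summary of device-related events up to Risser 5. Neither stops counting a subject's events at treatment failure.

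Table 7 in 11.1 lists the surgeries that are treatment failures. They include non-preventive revision, where the device is repositioned "or additional instrumentation is added to the original implant configuration", and removal of the whole system, whether or not it is replaced.

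On device deficiencies, 11.4 says: "All device deficiencies must be documented and submitted to Medtronic on the Device Deficiency eCRF".

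**The concern.** One limb of the overcorrection definition is a number of degrees. After a treatment failure the plan no longer asks for the measurement which that limb needs, although the event still belongs to the primary endpoint and the child may still be growing with a tether in place.

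The restriction suits the effectiveness endpoints. Protocol 13.3 and SAP 7.1.3.1 carry forward the last value before failure, so a later Cobb angle would not enter those analyses. The safety endpoints have no such rule, and events after failure count.

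Section 10.2.3 calls overcorrection the main risk of the procedure and relies on scheduled visits to find it: "This provides the Investigators the opportunity to detect and treat curve corrections that may be approaching overcorrection". At stake is complete ascertainment of one component of the primary endpoint in a study of 10 treated subjects.

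**Working it through.** The plan gives no figure to reproduce on this point. The check compares sections and then sets a scale.

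**1. Is a Cobb angle required after failure?** The reads named in 9.4.6.1 are the Risser score, device integrity and additional observations, all under a qualitative-only limit. A Cobb angle is quantitative and is not named. The schedule in Table 6 and the design text in section 6 list radiographic assessments at every follow-up visit without excepting failures, so they do not fully agree with 9.4.6.1. The separate Radiographic Evaluation Protocol was not available.

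**2. Which failures can leave a tether?** From Table 7:
- Non-preventive revision: a tether can remain.
- Removal with replacement: a tether can be present again.
- Removal without replacement: no tether.
- Fusion or extension of the fixation: a failure when done for progression of the initial scoliosis, which is the opposite direction from overcorrection.
- Cutting or loosening the braid for overcorrection: not a failure, so these children keep full follow-up.

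The gap therefore concerns mainly the first two groups.

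**3. Does the surgical limb of 9.4.5 close the gap?** Only in part. It needs surgery classified as treatment failure. If overcorrection after a failure is merely observed, or is handled by preventive braid surgery (not a failure under Table 7), the 20-degree limb is the only route to the definition.

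**4. Effect of one missed case.** Inputs: 10 treated subjects (9.1.1); 13.6.1 reports both events and subjects with an event.
- Event count: falls by 1 in every case.
- Subject rate: falls by 1/10 = 10 percentage points, only if the child has no other device-related event by 24 months.
- Exact (Clopper-Pearson) 95% intervals, an assumption because SAP 7.10.1 names no method: 1/10 gives 0.3% to 44.5%; 0/10 gives 0% to 30.8%. Losing a single case of this kind moves the upper limit by 44.5 − 30.8 = 13.7 points.

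**5. How often might this arise?** The documents give neither the number of failures nor an overcorrection rate after failure. For scale only, protocol 4.1 cites 13/116 = 11.2% in patients treated with other tethers. If that rate applied after failure, the chance of at least one overcorrection among k failures would be 1 − (1 − 13/116)^k:
- k = 1: 11%
- k = 2: 21%
- k = 3: 30%
- k = 4: 38%

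These are chances that an overcorrection occurs. The chance of missing one would be no higher, because some would be reported anyway.

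**6. Device deficiencies.** The list of retained safety items in 9.4.6.1 leaves them out. Table 6 footnote 2, the opening of section 11, and 11.4 require them without excepting failures, and 11.2 has unresolved ones reassessed at each required visit. Section 9.4.6.1 itself keeps the read of device integrity.

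**The case against.** The strongest reply is that 9.4.6.1 narrows what the study demands and does not forbid measurement. P/A films continue to maturity. Under 9.2.2 investigators evaluate images for adverse events and device deficiencies, and radiographic measurement follows site standard of care. A reversed curve could be entered as an additional observation, all adverse events remain reportable, and the surgical limb of 9.4.5 needs no angle. All of this stands. A reader might infer that overcorrection after failure goes unmeasured, or that the opportunity described in 10.2.3 is lost. The text supports only that the angle is not required.

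A reader might also infer that device deficiencies are under-counted after failure. The other sections still require them, so the omission is an inconsistency of wording and no under-count is shown.

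Three points on size also stand. Table 7 ties non-preventive revision to an adverse event to which the initial device position contributed, or to added instrumentation. Many such children may already count as having a device-related event, in which case only the event count would change. Multiplying 11.2% by all ten subjects to expect about 1.1 cases would be wrong, because the restriction touches only failures; with one or two failures the same assumption gives about 0.1 to 0.2. And nothing in the documents shows that children with a failed construct are at higher risk of overcorrection than the others.

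What the reply leaves unanswered is that a component of the primary endpoint is defined by a number that the plan stops requiring while events are still being counted.

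**Conclusion.** The point holds as a limited gap in ascertainment. After treatment failure the main thoracic Cobb angle is not required, so the 20-degree limb of the overcorrection definition may be under-detected in children whose failure left or restored a tether. Overt cases should still surface through films, adverse event reports or further surgery.

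The likely size is small and cannot be fixed from the documents, because the number of failures is not stated. The effect per missed case is the one in step 4 of the working, with its condition on the subject rate.

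The conclusion assumes that the qualitative-only limit in 9.4.6.1 overrides the general schedule and that the Radiographic Evaluation Protocol does not restore the measurement. The change is worth making because it is cheap and bears on the primary endpoint.

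**What to change.** Amend 9.4.6.1 so that, after a treatment failure, the main thoracic Cobb angle continues to be recorded from the P/A films already taken, until Risser 5. State that these values serve only the overcorrection test in 9.4.5 and the safety listings. Leave unchanged the carry-forward for the additional secondary endpoints in protocol 13.3 and SAP 7.1.3.1.

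In the same amendment, reconcile the list of retained safety items in 9.4.6.1 with Table 6 footnote 2, the opening of section 11, 11.2 and 11.4 on device deficiencies. Also make the radiographic schedule in Table 6 and section 6 agree with 9.4.6.1.

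The cost is a few extra measurements in a few subjects, plus an amendment with the submissions and approvals described in 9.8.3 and 15.7. No extra film or visit is needed. The case report forms and the Radiographic Evaluation Protocol may need a matching edit; they are separate documents and were not available.

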9.4.6.2. Relatedness of Subsequent Spinal Surgical Interventions

A relatedness determination will be made by the investigator to the original study device and the original study surgery to a subsequent surgical intervention.

For the purpose of harmonizing reports, each subsequent spinal surgical intervention will be classified according to five different levels of causality. The investigator will use the following definitions to assess the relationship of the subsequent spinal surgical intervention to the original study device (i.e., investigational device), other surgical components, or study procedures.

- Not Related: Relationship of the subsequent spinal surgical intervention to the original study device or study procedures can be excluded.
- Unlikely: The relationship with the use of the original study device or study procedures seems not relevant and/or the event can be reasonably explained by another cause, but additional information may be obtained.
- Possible: The relationship with the use of the original study device or study procedure is weak but cannot be ruled out completely. Alternative causes are also possible (e.g., an underlying or concurrent illness/clinical condition or/and an effect of another device, drug, or treatment). In cases where relatedness cannot be assessed, or no information has been obtained, the relationship should also be classified as possible.
- Probable: The relationship with the use of the original study device or surgical procedure seems relevant and/or the need for a subsequent spinal surgical intervention cannot reasonably be explained by another cause, but additional information may be obtained.
- Causal Relationship: The event is associated with the original study device or original surgical procedure beyond reasonable doubt.

A subsequent spinal surgical intervention determined as having “possible,” “probable,” or “causal” relationship to the Braive™ GMS will be conservatively considered as being “related” to the device.

9.5. Assessment of Effectiveness

9.5.1. Radiographic secondary endpoints

The radiographic secondary endpoints for this study are listed below. These endpoints are assessed as per site standard of care:

- Change from baseline in main thoracic Cobb angle at all available postoperative time points
- Change from baseline in proximal thoracic Cobb angle at all available postoperative timepoints
- Change from baseline in thoracolumbar/lumbar Cobb angle at all available postoperative timepoints

Medtronic Controlled Information

- Change from post-op baseline in Instrumented Cobb Angle at all available postoperative time points.
- Change from baseline in thoracic kyphosis at all available postoperative timepoints
- Change from baseline in Lumbar Lordosis at all available postoperative timepoints
- Change from baseline in coronal balance at all available postoperative timepoints
- Change from baseline in Sagittal Balance at all available postoperative timepoints
- Change from baseline in total vertical thoracic spine height (T1- T12) at all available postoperative timepoints
- Change from baseline in total vertical spine height (T1-S1) at all available postoperative timepoints

9.5.2. PedsQL (Pediatric Quality of Life Inventory™)

PedsQL will be evaluated prior to the study treatment.

The PedsQL Measurement Model is a modular approach to measuring health-related quality of life (HRQoL) in children and adolescents and those with acute and chronic health conditions. The 23-item PedsQL Generic Core Scales are designed to measure the core dimensions of health as delineated by the World Health Organization, as well as role (school) functioning. The 4 Multidimensional Scales are physical functioning, emotional functioning, social functioning and school functioning. The 3 Summary Scores are Total Scale score, Physical Health Summary score, and the Psychosocial Health Summary score. Two versions of this assessment will be filled out, one by the subject and one by the parent or legal guardian. Information from these versions will be analyzed separately.

9.5.3. SRS-22

The SRS-22 will be evaluated prior to the study treatment and postoperatively at 3 months, 6 months, 12 months, 18 months, 24 months and annually until skeletal maturity is reached.

The SRS-22 Patient Questionnaire has become the most widely used patient-reported outcome (PRO) instrument for evaluating individuals with idiopathic scoliosis. The SRS-22 contains 22 questions covering 5 domains: function/activity 5 items; pain 5 items; self-perceived image 5 items; mental health 5 items; and satisfaction with treatment 2 items. Each item is scored from 1 (worst) to 5 (best). Each domain has a total sum score ranging from 5 to 25, except for satisfaction, which ranges from 2 to 10. The sum of the first 4 domains gives a maximum subtotal of 100, and when the satisfaction domain is included, the maximum total is 110.

9.6. Imaging Guidelines

Study subjects are required to undergo imaging procedures at specified time points during the study. To ensure consistency in the type and quality of all images obtained throughout this study some requirements have been defined:

Medtronic Controlled Information

- Clinical sites must use imaging equipment (X-ray) that are maintained and calibrated according to the manufacturer's specifications when performing imaging procedures on subjects for this study.
- Imaging equipment maintenance and calibration will be monitored.
- To reduce the radiation exposure to study subjects, all X-ray examinations should be realized at the lowest radiation dose that still provides the minimally required image quality.

A Radiographic evaluation protocol will be kept separate from this document.

9.7. Recording Data

The investigator must ensure that the data reported in the eCRF and all other required study reports are accurate, complete and reported in a timely manner. Data reported on the eCRFs must be consistent with the source documents, and discrepancies between the eCRF and source documents need to be justified in writing, signed and dated by the investigator, and filed in the subject's medical file or appropriate location.

Subject neurological status and instrument accountability can be recorded directly on the eCRF and is considered source data. All other data entered in the eCRFs should be documented in the subject's medical records/source document (electronic or paper), (e.g., hospital records, surgery reports, x-rays, MRIs, CTs, or any other material that contains original information used for data collection including the documentation of AEs and study source document completed by the investigator or site staff). Subject/parent(s)/legal guardian completed questionnaires as well as data collected during subject/parent(s)/legal guardian phone calls will be considered as source data.

This study will be conducted using a Remote Data Capture (RDC) system. The RDC system allows the study centers to enter study data into the sponsor's database over a secure internet connection. Required data will be taken from source documents and directly entered into the study database by authorized site personnel in accordance with applicable regulations.

Every attempt should be made to complete the required onsite clinic visit. However, if the subject is unable to return to the investigational site for their scheduled follow-up visit, the study site can contact the subject and collect the following data remotely using the source document worksheet:

- SRS-22 – phone version or web-based application
- Adverse events and/or device deficiencies

The Principal Investigator or an individual delegated by the Principal Investigator on the Delegation of Authority Log is responsible for documenting and entering data for the study on the eCRFs. Only authorized site study staff can complete eCRFs. eCRFs shall be signed by the Principal Investigator or Sub-investigators (physicians only) as specified on the Delegation of Authority Log included in the Investigator Site File. The Principal Investigator or delegated Sub-Investigator is required to approve all data on eCRFs via electronic signature.

Procedures used for data review, database cleaning, and issuing and resolving data:

- Data will be reviewed using programmed and manual data checks.
- Data queries will be made available to centers for resolution.
- Study management reports may be generated to monitor data quality and study progress.

